11 INTERIM AND DMC ANALYSES

11.1 Interim Analysis

In the protocol it has been mentioned that IA may take place at any time during the study at the discretion of the sponsor to support regulatory and/or reimbursement dossiers. An interim analysis was conducted when the last subject reached Part A Week 24. The analysis details of the Week 24 interim analysis were provided in Section 11.1.1 below. Another IA will be conducted when the last subject reaches Part B Week 48, i.e., Week 144 in the OLE study. The analysis details of the Week 144 IA are provided in Section 11.1.2. Unless specified otherwise, the general rules, principles, and scopes specified in Section 10 apply to the IAs.

11.1.1 Week 24 Interim Analysis

For the following efficacy endpoints, the model-based main analysis was performed using the models specified in Section 10.3.1.2.2 with the Extended OLE Week 24 Visit windowing rule defined in Appendix F. Additional analyses was performed using the exact same model but with the regular Week 24 visit windowing rule defined in Appendix A. The descriptive summary for continuous efficacy endpoints also used the Extended OLE Week 24 Visit windowing rule.

- Absolute change in percent predicted forced expiratory volume in 1 second (ppFEV₁)
- Absolute change in sweat chloride (SwCl)
- Absolute change in CFQ-R respiratory domain (RD) score
- Absolute change in body mass index (BMI) and BMI-for-age z-score
- Absolute change in lung clearance index_{2.5} (LCI_{2.5})
- Absolute change in weight and weight-for-age z-score
- Absolute change in height and height-for-age z-score

The descriptive summary tables for continuous safety endpoints stayed with the regular OLE Week 24 Visit windowing rule defined in Appendix A and were restricted to the last visit at which the number of subjects was at least 10.

11.1.2 Week 144 Interim Analysis

The following efficacy endpoints will be analyzed using methods specified in Section 10.3.2.2.2. Both MMRM models and descriptive summaries will include data up to the OLE Part B Week 48 (inclusive) analysis visit. The windowing rules are provided in Appendix B.

- Absolute change in percent predicted forced expiratory volume in 1 second (ppFEV₁)
- Absolute change in sweat chloride (SwCl)
- Absolute change in CFQ-R respiratory domain (RD) score
- Absolute change in body mass index (BMI) and BMI-for-age z-score
- Absolute change in lung clearance index_{2.5} (LCI_{2.5})

- Absolute change in weight and weight-for-age z-score
- Absolute change in height and height-for-age z-score
- Pulmonary Exacerbation (PEx) and CF-related hospitalizations

The study is conducted during the COVID-19 pandemic. If extra assessments (e.g., unscheduled visits) will be collected to mitigate the impact of COVID-19 pandemic on this Week 144 IA, Extended OLE Part B Week 48 analysis visit may replace the regular OLE Part B Week 48 analysis visit for efficacy analysis, using the exact same analysis methods. In such situations, MMRM models with the regular OLE Part B Week 48 analysis visit may be conducted as additional analysis. All efficacy analysis for the Week 144 IA will be based on clinical assessed data.

The same definition on analysis period as described in Section 9 applies to this IA but the analysis period does not exceed the IA data cutoff date. The descriptive summary tables for continuous safety endpoints will stay with the regular visit windowing rule defined in Appendix A and will be restricted to the last visit at which the number of subjects is at least 10. For AE, PEx, similar event base parameters, all available data will be included.

11.2 IDMC Analysis

The IDMC's objectives and operational details will be defined in a separate document (IDMC Charter) which was finalized before the first subject first visit. The IDMC's planned safety reviews of study data are outlined in the IDMC Charter and IDMC Statistical Analysis Plan.

13 LIST OF APPENDICES

▪ Appendix A: Analysis Visit Windows for Safety and Efficacy Assessments

Table 13-1 Analysis Visit Windows for Safety and Efficacy Assessments for Part A			
Assessment	Visit ¹	Target Study Day	Analysis Visit Window (in study days) ²
Safety Assessment			
Serum Chemistry	Baseline	1	defined in section 8.1
Hematology	OLE Part A Week 8	57	[1, 85]
Vital Signs (excluding Weight, Height, BMI, and corresponding z-scores) ³	OLE Part A Week 16	113	(85, 141]
	OLE Part A Week 24	169	(141, 211]
	OLE Part A Week 36	253	(211, 295]
	OLE Part A Week 48	337	(295, 379]
	OLE Part A Week 60	421	(379, 463]
	OLE Part A Week 72	505	(463, 547]
	OLE Part A Week 84	589	(547, 631]
	OLE Part A Week 96	673	(631, 687]
	Safety Follow-up ⁴	Not applicable	Use nominal visit
Standard 12-lead ECG	Baseline	1	defined in section 8.1
Coagulation	OLE Part A Week 24	169	[1, 253]
	OLE Part A Week 48	337	(253, 421]
	OLE Part A Week 72	505	(421, 589]
	OLE Part A Week 96	673	(589, 687]
	Safety Follow-up ⁴	Not applicable	Use nominal visit
Efficacy Assessment			
Spirometry	Baseline	1	defined in section 8.1
Weight, Height and BMI (and the corresponding z-scores)	OLE Part A Week 8	57	(1, 85]
	OLE Part A Week 16	113	(85, 141]
	OLE Part A Week 24	169	(141, 211]
	OLE Part A Week 36	253	(211, 295]
	OLE Part A Week 48	337	(295, 379]
	OLE Part A Week 60	421	(379, 463]
	OLE Part A Week 72	505	(463, 547]
	OLE Part A Week 84	589	(547, 631]
	OLE Part A Week 96	673	(631, 687]
	Safety Follow-up ⁵	Not applicable	>687

Table 13-1 Analysis Visit Windows for Safety and Efficacy Assessments for Part A			
Assessment	Visit¹	Target Study Day	Analysis Visit Window (in study days)²
CFQ-R	Baseline	1	defined in section 8.1
	OLE Part A Week 8	57	(1, 113]
	OLE Part A Week 24	169	(113, 253]
	OLE Part A Week 48	337	(253, 421]
	OLE Part A Week 72	505	(421, 589]
	OLE Part A Week 96	673	(589, 687]
	Safety Follow-up ⁵	Not applicable	>687
Sweat chloride Lung Clearance Index IRT	Baseline	1	defined in section 8.1
	OLE Part A Week 24	169	(1, 253]
	OLE Part A Week 48	337	(253, 421]
	OLE Part A Week 72	505	(421, 589]
	OLE Part A Week 96	673	(589, 687]
FE-1	Baseline	1	defined in section 8.1
	OLE Part A Week 24	169	(1, 211]
	OLE Part A Week 48	337	(211, 505]
	OLE Part A Week 96	673	(505, 687]
Notes:			
¹ Visit name for analysis purpose is used to report data in tables and figures.			
² The analysis visit windows will be applied using the following rules for both scheduled and unscheduled visits:			
a. If no numerical measurement is available within a visit window, the measurement will be considered missing for the visit.			
b. If there is more than 1 numerical measurement available within a visit window, use the following rules:			
i. The measurement closest to the target day will be used; or			
ii. If there are multiple measurements with the same distance from the target day, the latest measurement will be used. If the latest measurement cannot be determined, then unscheduled visit will be selected.			
³ For measurement collected on the date of first dose of study drug in Treatment Period, if it cannot be determined whether the measurement is before or after the first dose:			
1. Scheduled measurement will be treated as pre-dose observation.			
2. Unscheduled measurement will be treated as post-dose observation.			
⁴ For safety Assessment, Safety Follow-up analysis visit will be based on nominal Safety Follow-up visit. If a subject doesn't have a nominal Safety Follow-up visit but has an ETT visit with study day >687, then the ETT visit will be mapped into Safety Follow-up analysis visit.			
⁵ For efficacy assessment, if a subject has nominal safety follow up visit with study day >687, then nominal Safety Follow-up visit will be mapped to Safety Follow-up visit; else if subject doesn't have a nominal safety follow-up visit with study day > 687 but has an ETT visit with study day >687, then the ETT visit will be mapped into Safety Follow-up analysis visit; else if there are multiple assessments with >687 then select the earliest record.			
Derived Variables:			

Table 13-1 Analysis Visit Windows for Safety and Efficacy Assessments for Part A			
Assessment	Visit¹	Target Study Day	Analysis Visit Window (in study days)²
1. Age (in years) at first dose date and post-baseline visit (for demographics, listing and the calculation of [percent] predicted spirometry variables):			
Obtain the age at informed consent in “yy, mm” format (e.g., 24 years, 6 months) in parent study from the Vital Signs (VS) page at the Screening Visit in parent study and add 0.5 month to convert to days.			
Obtain the informed consent date in parent study.			
Then age (in years) at first dose or post-baseline visit = [(first dose date or post-baseline visit date – informed consent date in parent study) in days + age at informed consent (in days) in parent study]/365.25.			
2. Age (in months) at first dose date and post-baseline visit (for use in calculation of BMI):			
Obtain the age at informed consent in “yy, mm” format (e.g., 24 years, 6 months) in parent study from the VS page at the Screening Visit in the parent study.			
Obtain the informed consent date in parent study.			
Then age (in months) at first dose or post-baseline visit = integer part of {[age at informed consent (in months) in parent study + 0.5 + diff(first dose date or post-baseline visit date, informed consent date) in months in parent study]} + 0.5.			
3. Missing first dose date or last dose date			
If the first dose date is missing, use Day 1 visit date.			
If the last dose date of study drug is not available and there is no data to indicate that the subject discontinued treatment, the data cutoff date will be used instead.			
If the subject discontinued treatment and the last dose date is missing or partial date is reported, the last dose date will be imputed based on, in descending order priority, the Early Treatment Termination (ETT) visit date, last visit date before the Safety Follow-up, or the last study drug administration date from EX SDTM domain, as appropriate. The imputation algorithm will ensure the imputed last dose date does not exceed the data cutoff date.			
4. Electrocardiogram:			
Baseline is defined in Section 8.1. If multiple ECG measurements are obtained on the same calendar day during the TE period,			
○ For summary purpose, the average value will be used as the ECG on that day;			
○ For threshold analysis purpose, all ECG values will be used			

Table 13-2 Analysis Visit Windows for Safety and Efficacy Assessments for the OLE study			
Assessment	Visit¹	Target Study Day	Analysis Visit Window (in study days)²
Safety Assessment			
Serum Chemistry	Baseline	1	defined in section 8.1
Hematology	OLE Part A Week 8	57	[1, 85]
Vital Signs (excluding Weight, Height, BMI, and corresponding z-scores) ³	OLE Part A Week 16	113	(85, 141]
	OLE Part A Week 24	169	(141, 211]
	OLE Part A Week 36	253	(211, 295]
	OLE Part A Week 48	337	(295, 379]
	OLE Part A Week 60	421	(379, 463]
	OLE Part A Week 72	505	(463, 547]
	OLE Part A Week 84	589	(547, 631]
	OLE Part A Week 96	673	(631, 715]
	OLE Part B Week 12	757	(715, 799]
	OLE Part B Week 24	841	(799, 883]
	OLE Part B Week 36	925	(883, 967]
	OLE Part B Week 48	1009	(967, 1051]
	OLE Part B Week 60	1093	(1051, 1135]
	OLE Part B Week 72	1177	(1135, 1219]
	OLE Part B Week 84	1261	(1219, 1303]
	OLE Part B Week 96	1345	(1303, 1359]
	Safety Follow-up ⁴	Not applicable	Use nominal visit
Standard 12-lead ECG	Baseline	1	defined in section 8.1
Coagulation	OLE Part A Week 24	169	[1, 253]
	OLE Part A Week 48	337	(253, 421]
	OLE Part A Week 72	505	(421, 589]
	OLE Part A Week 96	673	(589, 757]
	OLE Part B Week 24	841	(757, 925]
	OLE Part B Week 48	1009	(925, 1093]
	OLE Part B Week 72	1177	(1093, 1261]
	OLE Part B Week 96	1345	(1261, 1359]
	Safety Follow-up ⁴	Not applicable	Use nominal visit
Efficacy Assessment⁵			
Part A: same as in Table 13-1			
Part B: see below			

Table 13-2 Analysis Visit Windows for Safety and Efficacy Assessments for the OLE study			
Assessment	Visit¹	Target Study Day	Analysis Visit Window (in study days)²
Spirometry Weight, Height and BMI (and the corresponding z-scores)	Baseline	1	defined in section 8.1
	OLE Part B Week 12	757	(667, 799]
	OLE Part B Week 24	841	(799, 883]
	OLE Part B Week 36	925	(883, 967]
	OLE Part B Week 48	1009	(967, 1051]
	OLE Part B Week 60	1093	(1051, 1135]
	OLE Part B Week 72	1177	(1135, 1219]
	OLE Part B Week 84	1261	(1219, 1303]
	OLE Part B Week 96	1345	(1303, 1401]
	Safety Follow-up ⁶	Not applicable	>1401
CFQ-R	Baseline	1	defined in section 8.1
	OLE Part B Week 24	841	(667, 925]
	OLE Part B Week 48	1009	(925, 1093]
	OLE Part B Week 72	1177	(1093, 1261]
	OLE Part B Week 96	1345	(1261, 1401]
	Safety Follow-up ⁶	Not applicable	>1401
Sweat chloride Lung Clearance Index IRT	Baseline	1	defined in section 8.1
	OLE Part B Week 24	841	(667, 925]
	OLE Part B Week 48	1009	(925, 1093]
	OLE Part B Week 72	1177	(1093, 1261]
	OLE Part B Week 96	1345	(1261, 1401]
FE-1	Baseline	1	defined in section 8.1
	OLE Part B Week 48	1009	(667, 1177]
	OLE Part B Week 96	1345	(1177, 1401]
Notes:			
^{1,2,3} : See Table 13-1 .			
⁴ For safety Assessment, Safety Follow-up analysis visit will be based on nominal Safety Follow-up visit. If a subject doesn't have a nominal Safety Follow-up visit but has a Part A ETT visit with study day >687 or a Part B ETT visit with study day >1359, then the ETT visit will be mapped into Safety Follow-up analysis visit.			
⁵ For efficacy windowing rules, Part A data will only be used to derive Part A analysis visits using the window rules in Table 13-1 . Part B data will only be used to derive Part B analysis visits using the window rules in this table. Note that Safety Follow-up visits from both Parts will be combined for efficacy summary tables.			
⁶ For efficacy assessment in Part B, if a subject has nominal Part B safety follow up visit with study day >1359, then nominal Safety Follow-up visit will be mapped to Safety Follow-up visit; else if subject doesn't have a nominal safety follow-up visit with study day >1359 but has an ETT visit with study day >1359, then the ETT visit will be mapped into Safety Follow-up analysis visit; else if there are multiple assessments with >1401 then select the earliest record.			
Derived Variables: See Table 13-1 .			

Table 13-3 Efficacy Analysis Visit Windows for Week 144 Interim Analysis if Extended OLE Part B Week 48 is used.			
Assessment	Visit	Target Study Day	Analysis Visit Window (in study days)
Efficacy Assessment			
Part A: same as in Table 13-1			
Part B: see below			
Spirometry Weight, Height and BMI (and the corresponding z-scores)	Baseline OLE Part B Week 12 OLE Part B Week 24 OLE Part B Week 36 Extended OLE Part B Week 48	1 757 841 925 1009	defined in section 8.1 (667, 799] (799, 883] (883, 967] >967
CFQ-R	Baseline OLE Part B Week 24 Extended OLE Part B Week 48	1 841 1009	defined in section 8.1 (667, 925] >925
Sweat chloride Lung Clearance Index	Baseline OLE Part B Week 24 Extended OLE Part B Week 48	1 841 1009	defined in section 8.1 (667, 925] >925
Notes: The above analysis windows will be used only when mitigation plans regarding the impact of COVID-19 pandemic will be implemented. See Section 11.1.2 for details.			
See Table 13-1 table notes for detailed.			

▪ Appendix B: Imputation Rules for Missing Prior/Concomitant Medication Dates

Imputation rules for missing or partial medication start/stop dates are defined below:

1. Missing or partial medication start date:
 - a. If only DAY is missing, use the first day of the month.
 - b. If DAY and Month are both missing, use the first day of the year.
 - c. If DAY, Month and Year are all missing, use a date before the first dose date (in practical, use Jan. 01, 2000 to impute).
2. Missing or partial medication stop date:
 - a. If only DAY is missing, use the last day of the month.
 - b. If DAY and Month are both missing, use the last day of the year.
 - c. If DAY, Month and year are all missing, assign ‘continuing’ status to stop date (in practical, use Dec. 31, 2050 to impute).

In summary, the prior, concomitant, or post categorization of a medication is described below.

Table 13-4 Prior, Concomitant, and Post Categorization of a Medication

Medication Start Date	Medication Stop Date		
	< First Dose Date of Study Drug	≥ First Dose Date and ≤ End Date of TE Period	> End Date of TE Period
< First dose date of study drug	P	PC	PCA
≥ First dose date and ≤ End date of TE period	-	C	CA
> End date of TE period	-	-	A

P: Prior; C: Concomitant; A: Post

Imputation rules for missing and/or partial dates of non-pharmacological treatment/procedure will follow the same imputation rule.

▪ **Appendix C: Details of GLI Equations for Calculating ppFEV₁**

Percent predicted values will be calculated for parameters of FEV₁, FVC, FEV₁/FVC, and FEF_{25%-75%} using the Quanjer GLI-2012 Regression Equations and Lookup Tables.

The regression equations and lookup tables required to implement the Quanjer GLI-2012 predicted values are available in:

Philip H. Quanjer, Sanja Stanojevic, Tim J. Cole, Janet Stocks. Quanjer GLI-2012 Regression Equation and Lookup Tables (Version 7 April 2013). Global Lung Function Initiative. [online] Available at: <https://www.ers-education.org/guidelines/global-lung-function-initiative/spirometry-tools/it-engineers-and-manufacturers/> [Accessed Sep 22, 2020].

The instructions and tools on how to implement the Quanjer GLI-2012 equations are:

Philip H. Quanjer, Sanja Stanojevic, Tim J. Cole, Janet Stocks. Implementing GLI-2012 regression equations (Version 19 July 2015). Global Lung Function Initiative. [online] Available at: <https://www.ers-education.org/guidelines/global-lung-function-initiative/spirometry-tools/it-engineers-and-manufacturers/> [Accessed Sep 22, 2020].

Sanja Stanojevic. GLI-2012 - SAS Macro (Version 2, 7 April 2013). Global Lung Function Initiative. [online] Available at: <https://www.ers-education.org/guidelines/global-lung-function-initiative/spirometry-tools/sas-macro/> [Accessed Sep 22, 2020].

Data handling rule for spirometry is as follows:

- Input age and height with at least 2 decimal place
- Height collected at the respective visit should be used; if the height at the respective visit is not available, the last non-missing record will be used.
- For race, map the CRF reported Black or African American to Black, all other races in CRF (except White) are mapped to 'other'; multiple checks for race in CRF are also mapped to 'other'; white is a reference race in the equations and assumes 0 values for all race coefficients in the GLI equations.

▪ Appendix D: Imputation Rules for Missing AE Dates

Imputation rules for missing or partial AE start date are defined below. If the imputed AE start date is before the study informed consent/assent date, the AE start date will be imputed using the study informed consent/assent date. Ongoing events of the parent study will follow the imputation rule described in the SAP of parent study.

▪ If only Day of AE start date is missing:

- If the full (or partial) AE end date is NOT before the first dose date or AE end date is missing, then
 - if AE start year and month are equal to the month and year of first dose date, then impute the AE start day as the day of first dose date;
 - else impute the AE start day as 1.
- else impute the AE start day as 1.

Compare the imputed AE start date with TE period to determine whether the AE is pretreatment AE, TEAE or post-treatment AE.

▪ If Day and Month of AE start date are missing:

- If the full (or partial) AE end date is NOT before the first dose date or AE end date is missing, then
 - if AE start year is equal to the year of first dose date, then impute the AE start month and day as the month and day of first dose date;
 - else impute the AE start month as January and day as 1.
- else impute the AE start month as January and day as 1.

Compare the imputed AE start date with TE period to determine whether the AE is pretreatment AE, TEAE or post-treatment AE.

▪ If Year of AE start date is missing:

If the year of AE start is missing or AE start date is completely missing then query site.

- If the full (or partial) AE end date is NOT before the first dose date of the Treatment Period or AE end date is missing, then impute the AE start date as the first dose date.
- else impute the AE start date as the informed consent date.

Imputation rules for partial AE end date are defined below:

If partial end date, then impute as min (the last day of the month, data cut-off, end of study) if day is missing, or min (Dec, data cut-off, end of study) if month is missing.

▪ **Appendix E: Criteria for Threshold Analysis**

Table 13-5 Threshold Analysis Criteria for Laboratory Tests (as applicable)

Parameter	Threshold Analysis	Comments
Clinical Chemistry (LFT)		
ALT	>ULN to \leq 3xULN >3x to \leq 5xULN >5x to \leq 8xULN >8x to \leq 20xULN >20xULN	FDA DILI Guidance Jul 2009.
AST	>ULN to \leq 3xULN >3x to \leq 5xULN >5x to \leq 8xULN >8x to \leq 20xULN >20xULN	FDA DILI Guidance Jul 2009.
ALT or AST	(ALT>ULN to \leq 3xULN) or (AST>ULN to \leq 3xULN) (ALT>3x to \leq 5xULN) or (AST>3x to \leq 5xULN) (ALT>5x to \leq 8xULN) or (AST>5x to \leq 8xULN) (ALT>8x to \leq 20xULN) or (AST>8x to \leq 20xULN) ALT>20xULN or AST>20xULN	FDA DILI Guidance
Alkaline Phosphatase	>ULN to \leq 1.5xULN >1.5x to \leq 2.5xULN >2.5x to \leq 5xULN >5x to \leq 20xULN >20xULN	FDA DILI Guidance Jul 2009.
Total Bilirubin	>ULN to \leq 1.5xULN >1.5x to \leq 2xULN >2x to \leq 3xULN >3x to \leq 10xULN >10xULN	FDA DILI Guidance Jul 2009.
Direct Bilirubin	>ULN to \leq 1.5xULN >1.5x to \leq 2xULN >2x to \leq 3xULN >3x to \leq 10xULN >10xULN	FDA DILI Guidance Jul 2009.
Indirect Bilirubin	>ULN to \leq 1.5xULN >1.5x to \leq 2xULN >2x to \leq 3xULN >3x to \leq 10xULN >10xULN	FDA DILI Guidance Jul 2009.

Table 13-5 Threshold Analysis Criteria for Laboratory Tests (as applicable)

Parameter	Threshold Analysis	Comments
ALT and Total Bilirubin	ALT>3xULN and TBILI>2xULN	FDA DILI Guidance Jul 2009.
AST and Total Bilirubin	AST>3xULN and TBILI>2xULN	FDA DILI Guidance Jul 2009.
(ALT or AST) and Total Bilirubin	(ALT>3xULN or AST>3xULN) and TBILI>2xULN	FDA DILI Guidance Jul 2009.
GGT	>ULN to ≤2.5xULN >2.5x to ≤5xULN >5x to ≤20xULN >20xULN	CTCAE grade 1-4
Clinical Chemistry (NON-LFT)		
Albumin	<LLN to ≥30 g/L <30 to ≥20 g/L <20 g/L	CTCAE grade 1-3
Amylase	>ULN to ≤1.5xULN >1.5x to ≤2xULN >2x to ≤5xULN >5xULN	Criteria based upon CTCAE
Creatinine	>ULN to ≤1.5xULN >1.5x to ≤3xULN >3x to ≤6xULN >6xULN	CTCAE grades 1-4
Lipase	>ULN to ≤1.5xULN >1.5x to ≤2xULN >2x to ≤5xULN >5xULN	Criteria based upon CTCAE
Total protein	<LLN >ULN	No CTCAE
Creatine kinase	>ULN to ≤2.5xULN >2.5x to ≤5xULN >5x to ≤10xULN >10xULN	CTCAE grades 1-4
Hematology		
Hemoglobin	Hgb decreased (anemia) <LLN to ≥100 g/L <100 to ≥80 g/L <80 g/L Hgb increased >ULN to ≤20 g/L above ULN >20 g/L above ULN to ≤40 g/L above ULN >40 g/L above ULN	CTCAE grade 1-3 CTCAE grade 1-3

Table 13-5 Threshold Analysis Criteria for Laboratory Tests (as applicable)

Parameter	Threshold Analysis	Comments
Platelets	Platelet decreased <LLN to $\geq 75 \times 10^9 /L$	CTCAE grade 1-4
	<75 to $\geq 50 \times 10^9 /L$ <50 to $\geq 25 \times 10^9 /L$ $<25 \times 10^9 /L$	
	Platelet increased $>ULN$	No CTCAE available
Reticulocytes/Erythrocytes (%)	$<LLN$ $>ULN$	No CTCAE
Coagulation		
Activated partial thromboplastin time (PTT)	$>ULN$ to $\leq 1.5 \times ULN$	CTCAE grade 1-3
	>1.5 to $\leq 2.5 \times ULN$	
	$>2.5 \times ULN$	
Prothrombin time (PT)	$>ULN$ to $\leq 1.5 \times ULN$	CTCAE grade 1-3
International Normalized Ratio (INR)	>1.5 to $\leq 2.5 \times ULN$ $>2.5 \times ULN$	

Table 13-6 Threshold Analysis Criteria for ECGs

Parameter	Threshold Analysis	Comments
HR	Bradycardia ≤ 50 bpm	
	Tachycardia ≥ 140 bpm	
PR	≥ 220 ms and increase from baseline ≥ 20 ms	
QRS	≥ 120 ms	
QTc	Absolute values (ms) >450 ms (Male); >470 ms (Female) ≥ 500 ms	To be applied to any kind of QT correction formula.
	Increase from baseline Increase from baseline 30-60 ms Increase from baseline >60 ms	

Table 13-7 Threshold Analysis Criteria for Vital Signs

Parameter	Threshold Analysis	Comments
SBP	>120 mmHg	
	<70 mmHg	
DBP	>80 mmHg	
	<50 mmHg	

Table 13-7 Threshold Analysis Criteria for Vital Signs

Parameter	Threshold Analysis	Comments
Weight	Weight gain $\geq 5\%$ increase from baseline	
	Weight loss $\geq 5\%$ decrease from baseline	

▪ Appendix F: Analysis Visit Windows for Efficacy Assessments at Week 24 Interim Analysis

Table 13-8 Analysis Visit Windows for Efficacy Assessments			
Assessment	Visit¹	Target Study Day	Analysis Visit Window (in study days)²
Efficacy Assessment			
Spirometry	Baseline	1	defined in section 8.1
Weight, Height and BMI (and the corresponding z-scores)	OLE Week 8	57	(1, 85]
	OLE Week 16	113	(85, 141]
	Extended OLE Week 24	169	>141
CFQ-R	Baseline	1	defined in section 8.1
	OLE Week 8	57	(1, 113]
	Extended OLE Week 24	169	>113
Sweat chloride	Baseline	1	defined in section 8.1
Lung Clearance Index	Extended OLE Week 24	169	>1
Notes:			
¹ Visit name for analysis purpose is used to report data in tables and figures.			
² The analysis visit windows will be applied using the following rules for both scheduled and unscheduled visits:			
a. If no numerical measurement is available within a visit window, the measurement will be considered missing for the visit.			
b. If there is more than 1 numerical measurement available within a visit window, use the following rules:			
i. The measurement closest to the target day will be used; or			
ii. If there are multiple measurements with the same distance from the target day, the latest measurement will be used. If the latest measurement cannot be determined, then unscheduled visit will be selected.

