Blood biomarker sample	X			X		X	X		Section 11.4.2

^e Subjects whose Part B Day 1 Visit is on the same day or within 1 calendar day as the Part A Week 96 Visit do NOT have to repeat any Part B Day 1 assessments that were specified to be performed at the Part A Week 96 Visit. Subjects whose Part B Day 1 Visit is more than 1 calendar day after the Part A Week 96 Visit must complete all assessments specified for the Part A Week 96 AND Part B Day 1 Visits.

Table 3-1 Study VX19-445-107: Part A Treatment Period and Safety Follow-up Visit

Event/Assessment ^a	Part A Treatment Period (96 weeks)						Part A ETT Visit ^b	Part A Safety Follow-up Visit ^c (28 ± 7 Days After Last Dose of Study Drug)	Comments
	Day 1 ^d	Weeks 8, 16, 24, 36 (± 5 Days)	Weeks 4, 12, 20, 28, 32, 40, 44, 52, 56, 64, 68, 76, 80, 88, 92 (± 5 Days)	Week 48 (± 5 Days)	Weeks 60, 72, 84 (± 5 Days)	Week 96 ^e (± 5 Days)			
FE-1	X	Week 24		X		X	X		Samples may be collected by the subject's caregiver up to 24 hours before the study visit (e.g., at home). The sample may be collected pre- or postdose (Section 11.4.1).
IRT	X	Week 24		X	Week 72	X	X		Section 11.4.1
Study drug dosing	Day 1 through evening before Week 96 Visit								Subjects on study drug interruption at the end of the parent study may not begin dosing until they meet the criteria in Section 9.8. Refer to Section 9.6.1 for study drug administration details.
Study drug count		X		X	X	X	X		
Other events related to outcome	Continuous from signing of ICF through completion of study participation								Includes PEx, administration of antibiotic therapy for sinopulmonary signs/symptoms, and hospitalizations for CF (Section 11.3.6). Completion of study participation is defined in Section 9.1.5.
Medications review	Continuous from signing of ICF through completion of study participation								Completion of study participation is defined in Section 9.1.5.
Treatment and procedures review	Continuous from signing of ICF through completion of study participation								Completion of study participation is defined in Section 9.1.5.
AEs and SAEs	Continuous from signing of ICF through completion of study participation								Completion of study participation is defined in Section 9.1.5.

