9.2 Analysis Period for Part A Analysis

OLE Efficacy Period for Part A: Time from the first dose of study drug in the corresponding Part until the last efficacy assessment, which may be collected up to the corresponding Week 96 Visit or the earlier of Day 673 and the end of study participation if subject does not have the corresponding Week 96 Visit in the same Part. This analysis period will be used with the OLE-FAS for the corresponding Part to analyze efficacy data during the corresponding Part.

OLE Safety Period for Part A: Time from the first dose of study drug in the corresponding Part to 28 days after the last dose of the study drug in the corresponding Part or to the completion date of study participation (as defined in Section 9.1.5 of the CSP), whichever occurs first.

The completion date of study participation will be obtained from the end of study page of the eCRF.

The **Treatment-emergent (TE) Period for Part A** is same as the OLE Safety Period for the corresponding Part.

Cumulative TC Efficacy Period for Part A: For subjects who enrolled in Part A, the time from the first dose of study drug in the parent study (445-106 Part B) until the last efficacy assessment in Part A, which may be collected up to the Part A Week 96 Visit or the earlier of Day 673 in Part A and the end of study participation if subject does not have the Part A Week 96 Visit. For subjects who did not enroll in the OLE study and were enrolled and received study drug in the parent study, definition of this analysis period is the same as the parent study efficacy period.

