10.3 Efficacy Analysis

10.3.1 Efficacy Analysis for Part A

All efficacy analyses described in this section will be based on the OLE-FAS for Part A, unless otherwise specified. The analysis will include all available measurements through the last scheduled visit in Part A, including measurements after treatment discontinuation.

Continuous endpoints during the parent study will be analyzed using the same mixed-effects model for repeated measures (MMRM) approach as described in the SAP for the parent study. The resulting estimates will be identical to what is available in the final CSR of the parent study. Similarly, continuous endpoints during the OLE efficacy period for part A will be analyzed using a separate MMRM. The results obtained from the parent study and the OLE efficacy period for Part A will be displayed one followed by the other.

There is no multiplicity adjustment.

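### A Part A Week 96 efficacy visit on Day 688 or later is labelled Safety Follow-up or dropped, although SAP 9.2 and 10.3.1 include that visit whatever its day

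*SAP*

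**What the plan says.** **Windows.** SAP Table 13-1 sets the Part A Week 96 target at Day 673. The Week 96 efficacy window is (631, 687] for spirometry, weight, height and BMI; (589, 687] for CFQ-R, sweat chloride, LCI and IRT; and (505, 687] for FE-1. Only spirometry, growth and CFQ-R have a later row: Safety Follow-up, any day above 687.

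**Filling the follow-up row.** Footnote 5 works in order. First, "if a subject has nominal safety follow up visit with study day >687, then nominal Safety Follow-up visit will be mapped to Safety Follow-up visit". Failing that, an ETT visit after Day 687 is used. The last branch is "else if there are multiple assessments with >687 then select the earliest record".

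**Empty windows.** Note 2a to the table: "If no numerical measurement is available within a visit window, the measurement will be considered missing for the visit".

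**No recovery in Part B.** Table 13-2, footnote 5: "Part A data will only be used to derive Part A analysis visits using the window rules in" Table 13-1. The same footnote combines the Safety Follow-up visits of both Parts in the efficacy summary tables.

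**What counts as Part A efficacy data.** SAP 9.2 closes the Part A efficacy period with the subject's final measurement, "which may be collected up to the corresponding Week 96 Visit or the earlier of Day 673". The Day 673 limit, or the end of participation if sooner, is only for subjects without a Week 96 Visit. SAP 10.3.1: "The analysis will include all available measurements through the last scheduled visit in Part A, including measurements after treatment discontinuation".

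**Treatment status.** Protocol Table 3-1 gives dosing as "Day 1 through evening before Week 96 Visit". Under Protocol 9.1.1 that visit is Part B Day 1 for subjects who continue. Under 9.1.2, a subject who moves to Part B within 28 days of the last dose has no Part A Safety Follow-up Visit.

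**The concern.** The analysis period and the visit windows treat the same record differently. Section 9.2 admits a late Week 96 Visit as Part A efficacy data. Table 13-1 then gives it a follow-up label, or no label at all, purely because of its study day.

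Two outputs are affected. The Week 96 row, which is the last Part A estimate and the hand-over to Part B, loses a valid on-treatment value. The Safety Follow-up row, which a reader will take as off-drug, may gain an on-drug value. For a subject who rolls over within 28 days of the last dose, any Part A record in that row is on drug, barring an interruption, because that subject has no Part A follow-up visit. In the final tables, where follow-up visits of both Parts are combined, such a subject could supply both a mislabelled Part A record and a genuine Part B follow-up. The SAP gives no rule for choosing between them.

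**Working it through.** **1. The plan's own day counts.** Target day = 7 × week + 1.
- Part A Week 96: 7 × 96 + 1 = 673, as stated.
- Part B Week 96 (192 weeks from the start of Part A): 7 × 192 + 1 = 1345, as stated.

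**2. Late allowance for Week 96** (upper bound minus target).

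| Rows | Bound | Allowance |
|---|---|---|
| Part A efficacy, Table 13-1 | 687 | 14 days |
| Part A safety, Table 13-1 | 687 | 14 days |
| Part A chemistry, hematology, vital signs, Table 13-2 | 715 | 42 days |
| Part A ECG, coagulation, Table 13-2 | 757 | 84 days |
| Part B efficacy, Table 13-2 | 1401 | 56 days |
| Part B safety, Table 13-2 | 1359 | 14 days |

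**3. Which visits are affected.** The protocol window is 673 ± 5, or Days 668 to 678. The first affected day is 688, and 688 − 678 = 10 days beyond the window.

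**4. The rules applied to a nominal Week 96 Visit on Day 700, subject on drug.**
- Spirometry, growth, CFQ-R, with no later nominal follow-up or ETT visit (the rollover case): the record goes to Safety Follow-up. A single record gets there through the >687 row itself. The earliest-record branch matters only when there are several.
- The same assessments, with a nominal Safety Follow-up Visit after Day 687: that visit takes the slot, and the Week 96 record enters no by-visit result.
- Sweat chloride, LCI, IRT, FE-1: no window contains Day 700, so the record is unassigned in either case.
- Week 96 is then missing under note 2a, unless an unscheduled measurement lies inside the window. The preceding scheduled visits (Day 589 for spirometry and growth, Day 505 for CFQ-R, sweat chloride, LCI and IRT, Day 337 for FE-1) all lie outside it.
- In the final analysis, chemistry, hematology, vital signs, ECG and coagulation from that same Day 700 visit fall in the Part A Week 96 window (Table 13-2).

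**5. Where true follow-up visits fall.** The last dose is the evening before Week 96, and follow-up is 28 ± 7 days later.
- Week 96 on Day 673: last dose Day 672; follow-up on Days 672 + 21 = 693 to 672 + 35 = 707.
- Week 96 anywhere in its window: last dose Days 667 to 677; follow-up on Days 667 + 21 = 688 to 677 + 35 = 712.

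**6. Precision, by assumption.** The documents give no lateness rate. Suppose 5% to 10% of the 64 enrolled subjects (SAP 7.2), about 3 to 6, are affected.
- As a simple mean, the SE ratio is √(64/61) = 1.024 to √(64/58) = 1.050.
- The MMRM borrows from earlier visits. In a two-visit approximation with correlation ρ, the SE ratio is √[ρ² + (1 − ρ²) × 64/n]. With ρ assumed between 0.5 and 0.8, the inflation is about 0.9% to 1.8% for n = 61 and 1.8% to 3.8% for n = 58.

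**The case against.** **Day 687 has a logic.** It is the day before the earliest follow-up that can come after an in-window Week 96 Visit (Day 688), so it separates on-drug from off-drug records when visits are on schedule. That explains the bound. It does not settle the conflict with 9.2 and 10.3.1 for a visit that is late.

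**The case is rare and the stakes are modest.** The protocol expects visits within their windows. The endpoints are secondary or exploratory in a single-arm, open-label study. Both points stand and limit the weight of the finding.

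**Stronger readings that the documents do not support:**
- A reader might infer that the safety rows avoid the problem. They avoid the relabelling, because their follow-up row uses the nominal visit. But the Table 13-1 safety windows also close at Day 687, so a late safety value is also left out of the Part A Week 96 row in the Part A analysis.
- A reader might take Part B's 56 days as the plan's standard. The Part B safety rows end at Day 1359 (target + 14), and footnote 6 uses >1359 for nominal follow-up and ETT visits in Part B efficacy. The 1401 bound is thus itself at odds with its footnote.
- A reader might infer that much of the follow-up row would be on-drug values. That share needs the number of genuine follow-up records, which is not given, and pooling both Parts enlarges the row.
- A reader might infer from the COVID-19 text that late Week 96 visits are expected. The SAP describes alternative measures, a listing of impacted visits and extended windows for the interim analyses. It does not say that Part A Week 96 visits will be late.
- A reader might infer bias in the Week 96 estimate. Nothing in the documents shows that late attenders differ.

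**Conclusion.** The concern holds as an inconsistency within the SAP. For a Part A Week 96 Visit on Day 688 or later, the efficacy windows mislabel or discard data that 9.2 and 10.3.1 include, and in the final analysis they split one visit across different analysis labels. On-drug status rests on the protocol's dosing row and assumes no interruption.

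The effect is probably small. Only visits at least 10 days beyond the protocol window are touched, and their number is unknown. If 3 to 6 of 64 subjects were affected, the Week 96 SE would rise by a few percent at most, with about 5% as the simple-mean upper figure. The change is still worth making, because the rule is explicit, the lost or mislabelled values are valid, and the correction is a short edit.

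**What to change.** In the Table 13-1 efficacy rows:
- Assign the nominal Part A Week 96 record of a subject still on study drug to Week 96 whatever its day, for all efficacy assessments including sweat chloride, LCI, IRT and FE-1.
- Fill Safety Follow-up only from nominal Safety Follow-up visits, or from ETT visits that replace them. Delete the earliest-record branch of footnote 5 for any other record.

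Do not simply move the bound to Day 729 (673 + 56, copying Part B). True off-drug follow-up visits, at about Days 688 to 712, would then lie inside the Week 96 window and could be selected when no earlier record is there. Separation has to be by visit label, which footnotes 4 and 5 already use.

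**Cost.** A few lines of SAP wording. SAP 10.3.2 promises that the Part A estimates in the final analysis will be identical to those of the Part A analysis. If Part A outputs exist, their Week 96 and Safety Follow-up rows must be rerun and the change documented to keep that statement true. Because the data are open-label, the record should say that the window rule changed after those results were available.
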